5.5.4 Adverse Event Reporting

University of Rochester Medical Center Reporting - Serious adverse events that are associated with the study and occur while a subject is on study until 14 days after the date the subject goes off study must be reported in writing to the Strong Memorial Hospital IRB within 10 working days. They are also reported to the Data Safety Monitoring Committee within the same time frame. Adverse events that are both **unexpected fatal or life-threatening events** must be reported immediately to the IRB.

5.5.5 Data Safety Monitoring Plan

Investigators will conduct continuous review of data and patient safety. The review will include for each treatment arm level: the number of patients, significant toxicities as described in the protocol, dose adjustments, and responses observed. The Investigator will submit twice yearly summaries of this data to the Clinical Trials Monitoring Committee for review.

Clinical Trials Data Safety Monitoring Committee: The Director of the Cancer Center delegates responsibility for continued review and monitoring of all clinical trials conducted by the URCC to the Clinical Trials Data Safety Monitoring Committee. This committee provides oversight of study progress and safety by review of accrual and adverse events at annual meetings. Any adverse event requiring expedited review per protocol will be submitted to the Data Safety Monitoring Committee (DSMC) for determination as to whether further action is required. The study PI and the study medical monitor determine if the adverse event

requires expedited review. Interim meetings are scheduled, as needed, to address specific issues that require immediate attention to assure patient safety.

The Committee:

- a) Reviews assigned clinical trials conducted at the URCC for progress and safety.
- b) Reviews all adverse events requiring expedited reporting as defined in the protocol.
- c) Reviews reports generated by the URCC data quality control review process.
- d) Submits recommendations for corrective actions to the Protocol Review Committee and the PI
- e) In general, outcome data is not made available to individuals outside of the DSMC until accrual has been completed and all patients have completed their treatment. At this time, the DSMC may approve the release of outcome data on a confidential basis to the trial PI for planning the preparation of manuscripts and/or to a small number of other investigators for purposes of planning future trials. Any release of outcome data prior to the DSMC's recommendation for general dissemination of results must be reviewed and approved by the DSMC.

Safety Coordinator: The Medical Director of the Cancer Center Clinical Trials Office appoints the Safety Coordinator. The Safety Coordinator monitors adverse event rates utilizing the URCC Clinical Trials database. If any assigned study has had two or more of the same SAEs reported in a month or more than six of the same SAEs in six months, the DSMC will review the summary of SAEs, discuss events with the Study Chair, and conduct a more detailed review with the Study Chair. The Data Safety Monitoring Chair will determine if further action is required.

- 5.5.6 All study drugs will be dispensed and all biological specimens will be collected at the University of Rochester Medical Center.
- 5.5.7 There will be no cost to the patient for the study medication, the pathological tests, blood tests, or bone health tests. All costs will be paid from funds controlled by [name] within the James P. Wilmot

Cancer Center.

5.6 Walking and Progressive Resistance Exercise Arms 2 & 3

- 5.6.1 The Home-Based Walking and Progressive Resistance Exercise Program is designed by an Exercise Scientist certified by the American College of Sports Medicine (ACSM) and is in accordance with the guidelines for exercise testing and prescription as set forth by the ACSM.
- 5.6.2 The Home-Based Walking and Progressive Resistance Exercise Program will follow the guidelines listed below.
 - 5.6.2.1 The Home-Based Walking Prescription will be based on a patient's baseline pedometer assessment. [REDACTED]
 - 5.6.2.2 The Home-Based Progressive Resistance Prescription will be based on a patient's optimal level of challenge. Patients will be instructed on the proper use of resistance bands. [REDACTED]
 - 5.6.2.3 The study coordinator will talk with each patient on a weekly basis by telephone as a reminder to take calcitriol.

He/she will also answer any questions the patient may have regarding the exercise program in order to facilitate proper adherence and compliance to the exercise intervention.

- 5.6.3 All Walking and Progressive Resistance Exercises will be performed off-site from the University of Rochester Cancer Center in a home-based patient-selected environment.
- 5.6.4 There will be no costs to the patient for the physiological assessments (e.g. serum collection and muscular strength), resistance bands, pedometers, or Home-Based Walking and Progressive Resistance Exercise Prescription. All costs will be paid from funds controlled by [name] in the Behavioral Medicine Unit within the James P. Wilmot Cancer Center.

5.7 Commencement of a low to moderate walking and progressive resistance exercise program is not associated with any severe side effects and risks are minimal for individuals with no cardiopulmonary, orthopedic, or age-identified high risk factors as determined by the patient's treating physician (or designee). The chance of a cardiac event is rare once coronary disease has been excluded with reasonable certainty. Approximately 1 death per 15,000-20,000 healthy men per year occurs during jogging; this risk is much lower in women. A transient increase in blood pressure may occur with all types of exercise. Although unlikely, the risks involved in a low to moderate walking and progressive resistance exercise program are musculoskeletal—possibly mild muscle soreness, a muscle strain, or related injuries such as tripping. Overall, the risk level for participation in a low to moderate Home-Based Walking and Progressive Resistance program is minimal. Risks associated with a 6-minute walk test are similar to participation in a low to moderate walking exercise program and are minimal for individuals with no cardiopulmonary, orthopedic, or age-identified high risk factors as determined by the patient's doctor. 7-10 Repetition maximum tests for strength may cause minor stiffness and/or tenderness in muscles for a few days following testing. The nature of these assessments will require a level of exertion causing temporary changes such as an increase in heart rate and blood pressure, both of which are normal responses to moderate exercise. There is a small risk of irritation to the skin from the electrodes used for the BIA analysis. Lying under the canopy for resting metabolic testing creates a risk for some subjects to feel anxious or claustrophobic. Every effort will be made to minimize the risks for all study procedures through the approval of the treating physician to enter the study, supervision of all testing and exercise prescription by an American College of Sports Medicine certified Health and Fitness Instructor or a physician (or physician's designee) when necessary according to American College of Sports Medicine Guidelines, the use of standardized guidelines for exercise testing and prescription provided by the American College of Sports Medicine and resting metabolic rate testing and bioelectrical impedance analysis. Regarding the risks for resting metabolic testing, if patients feel claustrophobic during the resting metabolic test it will be stopped. Electrodes will be removed

immediately after the bioelectrical impedance test by the patient to minimize skin irritation. Risks will also be minimized by following the documented and approved procedures for the tests that are performed in the NIH-funded and approved University of Rochester General Clinical Research Center, and trained staff will perform these tests.

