7.2 Sample Size

7.2.1 Seventy-two women (18 women per treatment arm) were selected as an adequate size to provide pilot data for subsequent studies.

7.2.1.1 Based on the enrollment numbers above, the study will be able to detect a 40% difference in effects size between bone resorption and formation with 80% statistical power between the groups. Below is a graph of various effect sizes and the corresponding statistical power.

7.2.2 Based on a discussion with breast cancer clinicians at the University of Rochester Medical Center about patient volume and projecting an accrual rate of 50%, it will take approximately ten months to enroll 72 women.

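### The six-month SAE trigger in 5.5.5 adds essentially nothing to the one-month trigger, so a slow accumulation of the same SAE may not set off the automatic count-based DSMC review

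*Combined protocol and SAP*

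**What the plan says.** The Safety Coordinator paragraph of 5.5.5 sets two count triggers for a single study, joined by *or*. The first looks at one month and the second at six: given "two or more of the same SAEs reported in a month or more than six of the same SAEs in six months, the DSMC will" act. On either one, "the DSMC will review the summary of SAEs, discuss events with the Study Chair, and conduct a more detailed review with the Study Chair". The text does not say whether a month or six months is a calendar period or a rolling one. The first trigger counts by report; the second does not say whether it counts reports or event dates.

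Other routes to oversight stand beside this rule:

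- Section 5.5.4 requires study-associated SAEs to go to the IRB in writing within 10 working days, and adds: "They are also reported to the Data Safety Monitoring Committee within the same time frame". No count threshold applies.
- Section 5.5.5 gives the committee "review of accrual and adverse events at annual meetings", with interim meetings as needed.
- Events needing expedited review, as judged by the PI and medical monitor, are submitted to the DSMC.
- The investigator sends twice-yearly summaries by arm to a Clinical Trials Monitoring Committee. The document does not say whether this is the same body as the DSMC.

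On duration, 7.2.2 states that "it will take approximately ten months to enroll 72 women", and each woman is treated for 12 weeks (4.1.3).

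**The concern.** Two limbs of this kind normally do different jobs: the short window catches a cluster and the long window catches a slow build-up. Here the long-window count is so high that any series reaching it will already have tripped the short window. In effect the rule is only two in the same month.

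This is the only automatic, numeric, trial-level safety trigger in the visible text. The whole study lasts about 13 months, so the annual meeting may fall only about once. If the same SAE recurred at intervals among the women on calcitriol, nothing in the count rule would oblige the DSMC to look at those events together.

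**Working it through.** The documents state no operating characteristic for these triggers, so there is no figure of theirs to reproduce.

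**Inputs from the documents.** One-month trigger: at least 2. Six-month trigger: more than 6, so at least 7. Accrual: about 10 months (7.2.2). Treatment: 12 weeks, or 84 days (4.1.3). Women on calcitriol: arms 1 and 3, 2 × 18 = 36 of 72 (4.1.2). Study length: 84 / 30.44 = 2.76 months, and 10 + 2.76 = about 12.8 months.

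**Step 1: can the six-month trigger fire first?**

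- *Both windows by calendar.* With at most one event in each of six months, the total is at most 6, which is below 7. Full enumeration agrees: of the 792 ways to place seven events in six months, none has every month at one or fewer.
- *Both windows rolling, a month being two reports at most 30 days apart.* Escaping the one-month trigger needs six gaps of at least 31 days, and 6 × 31 = 186 days. Six months is at most 184 days, so escape is impossible.
- *One-month by calendar, six-month rolling.* Escape is possible. Events on 31 January, 28 February, 31 March, 30 April, 31 May, 30 June and 15 July (non-leap year) are seven in 165 days with one per calendar month. It is rare: at assumed Poisson rates of 0.5, 1.0 and 1.5 events per month over 13 months, the six-month trigger fires first in about 0.08%, 0.28% and 0.10% of simulated runs.

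**Step 2: how often does the whole rule fire?** The assumptions are mine. The number of women with the same SAE is Binomial(36, p); entry time is uniform over 10 months; event time is uniform over the 12 weeks after entry; the same SAE does not occur in the other arms. At p = 10% the expected count is 36 × 0.10 = 3.6.

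By calendar month, over 40,000 simulated trials:

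| True risk p | Rule fires |
|---|---|
| 5% | 12% |
| 10% | 38% |
| 15% | 64% |
| 20% | 82% |
| 30% | 97% |

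The six-month trigger fired alone in at most about 0.1% of trials at every risk.

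The undefined window matters. At p = 10%:

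| Quantity | Calendar month | Rolling 30 days |
|---|---|---|
| Rule fires | 38% | 55% |
| No trigger, given 4 or more identical SAEs | 37% to 38% | 15% |
| No trigger, given 6 or more | 14% | 1.8% |
| Rule fires if a count of 3 in six months is added | 64% to 65% | 67% |

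A hand check on the calendar column: four events spread evenly over 13 equal months avoid sharing a month with probability 12/13 × 11/13 × 10/13 = 1320/2197 = 0.60. Larger counts escape less often, which brings the average for four or more down.

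**Step 3: the extreme pattern.** Exactly one event per calendar month gives 6 in each aligned six-month period, so neither trigger fires. Over 12.8 months that is about 12 events (12/36 = 33% of the calcitriol women; 12/72 = 17% of all). With random arrivals averaging one per month, however, P(two or more in a month) = 1 − e⁻¹(1 + 1) = 0.264. The one-month trigger then fires within 6 months with probability 1 − 0.736⁶ = 84%, and within 13 months with probability 98%.

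**The case against.** A reader might infer that a steady one-per-month run of the same SAE would never come before the committee. The documents do not support that. Section 5.5.4 sends every study-associated SAE to the committee within 10 working days whatever the count, and 5.5.5 adds expedited review, annual and interim meetings and twice-yearly summaries. Only the automatic count-based escalation is lost. In part this answers the concern; it does not remove it, because single reports do not oblige anyone to review the events together and expedited review rests on judgement.

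A reader might also take the 12-event pattern as a realistic size for the gap. It needs near-perfect spacing. In 200,000 draws from the accrual model, 12 events escaped the calendar-month trigger 0.004% of the time, 10 events 0.26% and 8 events 3.7%. Large accumulations are caught by the first limb. The real gap lies at about three to six identical SAEs.

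Two further objections stand. The 38% describes how sensitive the one-month limb is at 3.6 expected events; the documents set no target that it fails, and it improves markedly if months are rolling. And the wording (assigned studies, the centre's own trials database) suggests an institutional rule, so changing it for this trial may need a trial-specific provision.

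**Conclusion.** The concern holds in a limited form. That the six-month limb is redundant is arithmetic: strictly so when both windows are calendar or both rolling, and with exceptions under 0.3% of runs when they are mixed. The consequence is that a slow accumulation of the same SAE may not set off the count-based DSMC review, while individual reporting and periodic review continue.

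The size depends on the assumed risk, the accrual and event-time model, and above all the undefined month. At a 10% risk among 36 women the rule fires in 38% to 55% of trials. With four or more identical SAEs, it stays silent in about 38% down to 15%. The redundancy itself depends on none of these assumptions about risk. It is a drafting defect in one safeguard among several, worth correcting because correction is cheap.

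**What to change.** Reconcile the two thresholds in 5.5.5. Leave the one-month limb, and have the DSMC set a six-month count that the one-month limb does not already imply, which means six or fewer. The choice should rest on operating characteristics for a study with 36 women on calcitriol, since counts near six would add little when only a few events are expected. For illustration only, at a 10% risk by calendar month, a count of three raises the chance of a review from 38% to about 64% to 65%, and a count of four to about 47%. By rolling 30 days, a count of three raises it from 55% to 67%.

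State for both limbs whether the window is calendar or rolling, and whether it runs on report date or event date. If the present rule is institutional, write the new count as a rule for this trial.

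The cost is a short text change and an occasional extra committee review, which does not itself stop the trial.

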5.8 Multivitamin Arm

5.8.1 New Formula Centrum®

Study participants assigned to arm #4 will receive a daily multivitamin and mineral supplement. They will be instructed to take one (1) tablet of New Formula Centrum® (Wyeth Consumer Healthcare) daily for the duration of the intervention. The supplement contains: Vitamin A 3500 IU (70% Daily Value (DV)), Beta-Carotene 25 µg, Vitamin C 90 mg (150% DV), Vitamin D 10 µg (100% DV), Vitamin E 30 IU (100% DV), Vitamin K 25 µg (31% DV), Thiamin 1.5 mg (100% DV), Riboflavin 1.7 mg (100% DV), Niacin 20 mg (100% DV), Vitamin B₆ 2 mg (100% DV), Folic Acid 500 µg (125% DV), Vitamin B₁₂ 6 µg (100% DV), Biotin 30 µg (10% DV), Pantothenic Acid 10 mg (100% DV), Calcium 200 mg (20% DV), Iron 18 mg (100% DV), Phosphorus 109 mg (11% DV), Iodine 150 µg (100% DV), Magnesium 100 mg (25% DV), Zinc 11 mg (73% DV), Selenium 55 µg (79% DV), Copper 0.9 mg (45% DV), Manganese 2.3 mg (115% DV), Chromium 35 µg (29% DV), Molybdenum 45 µg (60% DV), Chloride 72 mg (2% DV), Potassium 80 mg (2% DV), Boron 150 µg, Nickel 5 µg, Silicon 2 mg, Tin 10 µg, Vanadium 10 µg, Lutein 250 µg, and Lycopene 300 µg. Patients will be provided with the first 6 weeks worth of multivitamins at the start of the trial and the remainder of the multivitamins at the week 6 visit. There are no dietary restrictions for participants assigned to this arm. Participants assigned to this arm who normally use calcium supplementation are free to continue.

6.0 Treatment Evaluation

6.1 Measures

6.1.1 Bone health

6.1.1.1 Levels of bone resorption will be measured by **Cross-linked N-teleopeptide of type I collagen (NTx)**. NTx is a specific indicator of bone resorption. It is generated from bone by osteoclasts as a degradation product of type I collagen, and it can easily be measured in urine or serum. NTx is a valid and reliable measure of bone resorption.¹⁵⁶ Researchers believe that markers of bone resorption are superior to markers of bone formation and more accurately predict changes in bone mass.¹⁵⁷ Bone resorption markers are also able to predict failing bone health in advance of BMD. Laboratory assay methods of NTx levels are well

established and considered reliable.¹⁵⁸

6.1.1.2 Levels of bone formation will be measured by **bone-specific alkaline phosphatase (BAP)**. Bone formation markers, specifically (BAP), are also considered a valid measure of bone health.^{159, 160} Although BAP is a valid measure of bone health, measures of bone resorption tend to be better predictors of bone health. Laboratory assay methods of BAP levels are well established and considered reliable.¹⁶¹

6.1.2 **Physical activity** will be assessed subjectively using the Aerobic Center Longitudinal Study Physical Activity Questionnaire and questions on the daily journal. In addition, objective assessments of physical activity will be obtained via the pedometer.

6.1.2.1 The **Aerobic Center Longitudinal Study Physical Activity Questionnaire (ACLS)** is a measurement instrument that includes assessment of lifestyle physical activity. The questionnaire requests that participants report their engagement (frequency, intensity and duration) in fourteen different physical activities over the last three months. Estimates of energy expenditure are calculated using the following equation: (sessions/week) * (min/session)* (hour/min) * MET [Note: MET = metabolic energy expenditure rate] for each activity and then summed to provide total MET hours of energy expenditure for a week. The index of walking, jogging, and running predicted treadmill performance time $\beta = 0.31$ and there is a moderate relationship between energy expenditure estimates and treadmill performance ($r = 0.41$). The accuracy and reliability of the ACLS has been previously demonstrated.¹⁶²

6.1.2.2 The **Pedometer** device will be used to assess duration of physical activity via steps walked during the time out of bed. [Note: Participants NOT assigned to the exercise arm will give back their pedometer after the 5-day baseline measure and will have the pedometer reissued for the 5-day measure at the end of the trial.]

6.1.2.3 The **Daily Journal** is designed to track daily physical activity. The participant will be asked to complete the journal each night immediately prior to sleeping and record steps and miles walked, caloric expenditure, and a Rating of Perceived Exertion.

6.1.3 Aerobic capacity will be assessed using a **VO2max Treadmill Test** as a measure of compliance using a modified “Branching Treadmill Protocol”. Participants begin at a normal walking speed (2.5 mph) and 0% grade.

After 2 min. the speed is increased to a faster walking speed (3.0 mph) and 0% grade. After 2 min, the speed is increased to 3.5 mph and 2% grade. Thereafter, only the grade is increased by 2% every 2 min. Oxygen consumption (VO₂), carbon dioxide production (VCO₂), and flow rate will be measured continuously. The test is ended when the participant wants to stop. An MD is available onsite in the hospital during all tests as outlined by the ACSM fitness testing guidelines. In preparation for the exercise treadmill test, subjects will be instructed to fast for 4 hrs prior to the test and they will be asked to rest quietly on a bed in a quiet room for 30 minutes under a clear canopy which is placed over their head. During this 30 minute period, they will have their resting metabolic rate measured for 30 minutes using continuous, computerized open-circuit indirect calorimetry (Sensormedics® Vmax). A 6-Minute walking test may be substituted for the treadmill test in the event the person is not able to complete it. This is a sub maximal measurement using a 6 minute walk protocol. Participants are given a short warm up and cool down walking protocol in the test walking area in the University of Rochester. Participants walk for a total of 6 minutes and cover as much distance as they can during this time. Upon completion of the test, the total distance walked is used to calculate an estimate of aerobic capacity (VO_{2max}:Maximal Oxygen Consumption).

6.1.4 **Muscular fitness** will be assessed using two measures: a handgrip dynamometer test and a 7-10 repetition maximum strength test.

6.1.4.1 The **Handgrip Dynamometer Test** is a grip strength test used to assess the maximal voluntary contraction generated by the arm muscles. The test is administered with the patient standing in anatomical position, the elbow joint angle will be held constant at 180 degrees with the medial distal humeral epicondyl held 2 inches from the torso. Trials will be performed in an alternating bilateral sequence for a total of six attempts (three with each arm). The best score of the three trials will be used for right and left limbs to calculate static strength. The surgically involved arm(s) will be noted for data analysis. The handgrip dynamometer test has been previously used in a number of URCC CCOP protocols and has shown to be a reliable clinical method of assessing strength.¹⁶³

6.1.4.2 The standard **7-10 Repetition Maximum Dynamic Strength Testing Protocol** will be used to estimate patients' 1-repetition maximums for the leg extension (quadriceps) and bench press (pectoralis and deltoid). The patients will receive a full orientation to the fixed resistance machines and proper lifting form by a certified (ACSM) exercise testing professional. Participants will perform a light warm up consisting of 8 lift repetitions employing the lightest weight on the machine. After the warm up, patients

will be given a 2-3 minute rest break. A weight will be selected by the exercise testing staff based on the ease or difficulty of completing the warm up for each patient, and this weight will be lifted until subjective fatigue. Alternating rest breaks (2-3 minutes) and lifting bouts will continue with the resistance weight adjusted by the exercise testing staff until the patient reaches a level of resistance that results in subjective fatigue between 7-10 repetitions. Established algorithms employing the weight lifted and the number of repetitions completed will then be used to estimate the patients' 1-repetition maximum.¹⁶⁴ The 7-10 Repetition Maximum Dynamic Strength Testing Protocol has been previously used in a number of URCC CCOP protocols and is used by ACSM as a method of assessing strength.¹⁶⁵

6.1.5 Skeletal muscle mass is assessed using the following measure:

6.1.5.1 The **RJL Bioelectrical Impedance System** is a non-invasive, easy-to-administer and safe method of assessing lean body mass. BIA involves passing a small electrical current through the body and evaluating the reactance and resistance to flow, which are related to fat-free mass (FFM) and total body water. Prediction of lean body mass from BIA is as reliable as skin-fold measurements and hydrostatic weighing. Participants need to be 4-hours fasted, abstained from physical exercise for 12 hours, abstained from alcohol and diuretics (unless prescribed) for 48 hours, well hydrated (water only), and voided completely prior to assessment. Participants lie supine on a flat surface for approximately 5 minutes prior to the test to ensure a resting metabolic state. Electrodes are attached to the right hand (distal end of the 3rd and 4th metacarpal and distal end of the ulnar and radius) and the right foot (distal end of the 3rd and 4th metatarsal and distal end of the tibia and fibula). Skeletal muscle mass will then be calculated from the lean body mass.¹⁶⁶ BIA is considered an accurate and reliable test in determining skeletal muscle mass among the general population, including older adults.¹⁶⁷⁻¹⁶⁹

6.1.6 For the resting metabolic rate, subjects will be instructed to fast for 4 hrs prior to the test, and they will be asked to rest quietly on a bed in a quiet room for 30 minutes under a clear canopy which is placed over their head. During this 30 minute period, they will have their resting metabolic rate measured for 30 minutes using continuous, computerized open-circuit indirect calorimetry (Sensormedics[®] Vmax).

6.1.7 Gait and balance is assessed using the following measure:

6.1.7.1 The **Tandem Walk Test (TWT)** is a non-invasive, easy-to-administer, and safe method of assessing gait. The TWT involves

testing a woman's ability to walk with the heel of her front foot touching the big toe of her rear foot.^{170, 171} The scores for this test are: 1=able to do four consecutive tandem steps; 2=unable to do four consecutive tandem steps without stepping off or touching the examiner's arm; 3=unable or unwilling to put feet in tandem position. Women who use walking assistance and do not take the test will be assigned a score of 4.

